The objective of this study is to develop a brief, culturally sensitive face-to-face smoking cessation intervention for Hispanic construction workers and conduct a pilot two-arm, cluster-randomized clinical trial (RCT) to test the developed intervention for acceptability and potential efficacy- A two-arm, cluster-randomized controlled trial will be conducted with at least 14 construction sites (dependent on how many smokers can be recruited from each site), selected from one Construction Company in south Florida. Cluster randomization is used with construction site chosen as the unit of allocation because it is most practical in this setting and minimizes the risk of spillover effects from the intervention to the control group. Computer-generated random selection will be used to randomize construction sites. Then, construction sites will be randomly assigned to the intervention (enhanced care) or the control group (usual care), and study participants working in these sites will receive treatment accordingly. In conjunction with the site safety manager, we will recruit at least 126 adult Hispanic construction workers who smoke ≥ 5 cigarettes/day. Participants in the enhanced care will receive one culturally adapted brief face-to-face behavioral counseling session developed in phase 1 and delivered during breaks, two brief follow-up phone counseling calls, fax referral to the Florida quitline (QL), and provision of up to 8 weeks of free NRT. Participants in the usual care will receive fax referral to the Florida QL, and provision of up to 8 weeks of free NRT. *Main outcomes* include: 1) estimating yield (number of workers available divided by number eligible; and number eligible divided by number randomized), 2) facilitators and barriers to delivering the intervention in the proposed setting, 3) willingness of participants to be randomized and acceptability of the intervention, 4) follow-up rates, response rates to questionnaires, adherence/compliance rates, and the time needed to collect and analyze data, 5) QL enrollment rates, and 6) exploring the willingness of the target population in involving in the research design and conduct. *Potential efficacy* outcomes include the difference in prolonged abstinence, and point-prevalence abstinence rates at 6-month follow up confirmed by saliva cotinine $< 15\text{ng/ml}$.

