Recruitment, Study Participants, and Procedures- Our target sample size is up to 150 Hispanic smokers. We will coordinate with the safety managers of the participating construction sites to identify smokers who are interested in quitting smoking and arrange a visit to meet these workers. On day 1, two bilingual PH graduate assistants will approach these workers during their break to explain the study, complete the screening, and then obtain the consent form from those who are eligible. To participate in the study participant should be Hispanic male construction workers on site who are \geq 18 year old and have smoked \geq 5 cigarettes/day in the past year. Additionally, potential participants need to be available on site in the following two days, have access to telephone, have no plans to move in the next six months, and be interested in making a serious quit attempt in the next 30 days, and have no contraindication to NRT. Exhaled carbon monoxide levels and saliva cotinine will be tested among eligible participants to verify the self-reported smoking status. Individuals who decline to participate or who are ineligible (e.g., non-Hispanics, women) will be referred to the QL and provided with brochures that include information about the QL contact number and services. They will also be given a flyer about the UM Quitville smoking cessation study for which they may be eligible (only for English speakers). Those who are potentially eligible and interested in participating in the study will sign a consent form, then undergo a baseline screening to confirm eligibility and to collect information about: demographics, job characteristics, acculturation,⁴¹ smoking history, nicotine dependence,⁴² stages of change,⁴³ quit ladder,⁴⁴ smoking self-efficacy,⁴⁵ depression,⁴⁶ social support,⁴⁷ exposure to secondhand smoke, and quality of life. All questionnaires, informed consent, and educational materials will be available in English and Spanish and will be administrated by the bilingual graduate assistants. After completing the baseline assessment, a second visit in the following day will be scheduled to provide the intervention. If time does not permit to complete the entire baseline assessment, the exhaled carbon monoxide and saliva cotinine test, demographics and smoking behavior questions will be administered on-site and the remainder will be given to the

STUDY PROTOCOL AND ANALYSIS PLAN

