participant to be completed. Participants will receive a text-message reminder about the second visit at the evening. If time permits on the first day of recruitment to deliver the intervention, all aspects will be completed on that day rather than on day 2. [name], who has years of experience in training and supervising cessation trials,^{37,38,48} will be responsible for the training of PH graduate students in recruitment and conduct of the cessation trial such as 1) human subjects protection, 2) consequences of smoking, 3) motivational strategies, 4) pharmacotherapies used in smoking cessation, and 5) the study's protocol. Photographs and/or video may be taken during the sessions to be used for progress reports and presentations.

Participants in the **Usual Care** will receive up to six week supply of NRT, brochures about the QL services, and will be referred to the QL using the “fax referral form”. Participants will be informed that the QL is free, and the QL counselor will work with them to devise a specific plan to quit smoking and will arrange the delivery of free 2-week NRT for their quit attempt. Participants will have access to free NRT for a total of eight weeks (2-week supply from the QL, and 6-week supply from the study).

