Outcome Measures- This pilot study aims to explore the acceptability potential and efficacy of the developed intervention compared to QL. *Main outcomes* include: 1) estimating yield (number of workers available divided by number eligible; and number eligible divided by number randomized), 2) facilitators and barriers to delivering the intervention in the proposed setting, 3) willingness of participants to be randomized and acceptability of the intervention, 4) follow-up rates and response rates to questionnaires, adherence/compliance rates, and the time needed to collect and analyze data, and 5) exploring the “willingness” of the target population to be involved in the research design and conduct.⁶⁰⁻⁶² *Potential efficacy outcomes* will focus on comparing prolonged abstinence (defined as no smoking, not even a puff, after a grace period of two weeks after quit date), and point-prevalent abstinence (defined as self-report of not smoking in the past 7-days; not even a puff) confirmed

STUDY PROTOCOL AND ANALYSIS PLAN

by saliva cotinine level of <15ng/ml at 6-month between the two study arms. For individuals who do not quit entirely, the decrease in smoking (i.e., cigarettes/day) will be assessed.^{63,64} Relapse is defined as smoking at least once/week on two consecutive weeks.⁶⁵ Secondary outcome measures will focus on differences in stage of change/readiness to quit,⁶⁶ and treatment adherence according to intervention assignment.³⁷

All participant data will be coded with an identification number and only approved personnel will have access to the key linking identification numbers with participant names. Data will be stored and managed in REDCap and accessed only by approved study personnel. Paper interview instruments will be stored in a locked filing cabinet.

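### Nothing conceals a site's arm while its workers are being recruited, so knowledge of the arm could influence who enrols

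*Combined protocol and SAP*

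**What the plan says.** The objectives statement and the Design paragraph of Section 5 make the site the unit of allocation. After sites are assigned, "study participants working in these sites will receive treatment accordingly". No individual allocation step after consent is described.

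Section 5, under Recruitment, Study Participants, and Procedures, sets out how workers enter:

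- Candidates are found through site management: "We will coordinate with the safety managers of the participating construction sites to identify smokers who are interested in quitting smoking".
- On day 1, "two bilingual PH graduate assistants will approach these workers during their break to explain the study, complete the screening", and then take consent. One eligibility item is a matter of judgement: whether the worker is seriously interested in trying to quit within 30 days.
- Treatment is scheduled for the following day by default, with an exception: "If time permits on the first day of recruitment to deliver the intervention, all aspects will be completed on that day".
- If time is short, only exhaled CO, cotinine, demographics and smoking behaviour must be collected on site. The worker may complete the rest of the baseline later.

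The main outcomes listed under Outcome Measures in Section 7 include "willingness of participants to be randomized and acceptability of the intervention".

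**The concern.** Random allocation of sites protects the choice of sites. It does not protect the choice of workers within a site if the people choosing, or the workers deciding, know the arm. The safety manager may put forward different men, the assistants may judge quit interest differently, or workers may be more or less ready to sign. The arms can then differ in motivation before treatment starts, and site randomization does not correct that.

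Two results are at stake. One is the 6-month abstinence comparison, which the Sample Size paragraph says will help to estimate the effect for a full-scale trial. The other is the feasibility evidence, which is the pilot's main purpose. Agreeing to join a site whose arm is already known is not the same as agreeing to be randomized, and the yield figures depend on the same enrolment decisions.

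**Working it through.** **1. Is the arm fixed before recruitment?** The objectives statement describes site assignment first and recruitment with the safety manager next. That order implies allocation first, but no section gives a date or an explicit sequence relative to consent.

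**2. Can the arm be seen while recruitment continues?** Three statements bear on this:

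- The arm belongs to the whole site (objectives; Section 5, Design).
- Treatment may be given on the recruitment day (Section 5, Recruitment).
- The Enhanced Care session takes place at the lunch truck (Section 5), and recruitment takes place at morning or noon breaks in partnership with the lunch truck (Section 10).

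Once one worker has been counselled, the site's arm can be known to staff and co-workers for everyone recruited there later. This holds even if that first worker consented without knowing the arm.

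**3. Does anything prevent or correct this?** No section describes concealment from safety managers, assistants or workers. The Data Analysis section compares cessation by chi-square and states no baseline adjustment of the arm comparison. Intention-to-treat analysis and biochemical confirmation act after enrolment. Stage of change and quit ladder could show an imbalance in motivation, but they are outside the guaranteed on-site set and may be answered after the arm is known.

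**4. Scale.** The plan gives no figure for this bias, so there is none to reproduce. The yardstick is Section 11: 25% in the intervention arm against 15% or 10% in control, which is a difference of 10 or 15 points. Its stated powers do reproduce. With 7 sites × 7 workers = 49 per arm, power is 23.3% and 49.8% without a design effect, against 23% and 50% stated. With 1 + (7 − 1) × 0.01 = 1.06 it is 22.2% and 47.5%.

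Spurious difference = share of one arm's recruits replaced × (quit rate of those who come in − quit rate of those they replace). All inputs below are assumptions, with 10% as the replaced workers' rate:

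| Share replaced | Incoming rate 25% | Incoming rate 30% |
|---|---|---|
| 10% | 0.10 × 0.15 = 1.5 points | 0.10 × 0.20 = 2.0 points |
| 20% | 0.20 × 0.15 = 3.0 points | 0.20 × 0.20 = 4.0 points |
| 30% | 0.30 × 0.15 = 4.5 points | 0.30 × 0.20 = 6.0 points |

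**5. Effect on the test.** Take no true effect, 63 per arm and 126/14 = 9 workers per site. The design effect is 1 + (9 − 1) × 0.01 = 1.08 and the effective size is 63/1.08 = 58.3 per arm. Let b be the spurious difference and SE its standard error. The two-sided false-positive rate is Φ(b/SE − 1.96) + Φ(−b/SE − 1.96). Suppose the share of more motivated recruits differs between arms by 10, 20 or 30 points, centred on 50%:

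- Quit rates 10% v 25%: b = 1.5, 3.0, 4.5 points; false-positive rate 5.5%, 7.1%, 9.8%.
- Quit rates 5% v 30%: b = 2.5, 5.0, 7.5 points; 6.5%, 11.0%, 18.8%.
- Quit rates 10% v 40%: b = 3.0, 6.0, 9.0 points; 6.6%, 11.7%, 20.4%.

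**The case against.** A reader might infer that same-day delivery proves recruiters know the arm before consent. It does not: a team can consent workers, finish baseline, then open the assignment and treat that afternoon. Carrying supplies need not reveal the arm either, because NRT, quitline brochures and the fax referral are common to both arms. A reader might also infer that the recruiting assistants deliver the counselling. They are trained for both recruitment and trial conduct, but no section names who delivers the session. Nor does any section say that workers are told their arm before consent. The consent pages are not in the public text, so their content cannot count against the plan. These points stand, and neither stronger reading should be asserted.

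There are also partial safeguards. Eligibility, NRT and quitline referral are the same in both arms, every recruit must already be interested in quitting, smoking status is checked at entry, and baseline characteristics are compared. These narrow the room for selection but do not close it.

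Finally, a bias of a few points is small beside the sampling error. With 63 per arm and no design effect, the 95% half-width is 1.96 × √[(0.10 × 0.90 + 0.25 × 0.75)/63] = 13.0 points, or 13.9 points with 15% in control. That is true of the test in this pilot. It is a weaker defence for an effect estimate meant to inform a larger trial, since bias does not average out, and it does not touch the willingness outcome.

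What the objection leaves intact is that the arm is a property of the site. Treating one worker on day 1 can disclose it to all later recruits there, and nothing in the plan guards against that.

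**Conclusion.** The concern holds as a risk built into the procedures, not as a demonstrated bias. As written, the plan lets a site's arm become known while its workers are still being identified, screened and consented. The abstinence comparison could be biased, and willingness to be randomized becomes partly willingness to accept a known arm.

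A reader might take the illustration to mean a bias of 3 to 4 points in favour of Enhanced Care. The documents support neither the size nor the direction; knowing the arm could equally draw less motivated workers into Enhanced Care. The range of 1.5 to 6 points rests wholly on the assumed replacement shares and quit rates, and is 15% to 60% of a 10-point difference or 10% to 40% of a 15-point one. The conclusion also rests on reading the order of the objectives statement as allocation before recruitment.

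**What to change.** - Keep each site's assignment sealed, by envelope or a REDCap release, from recruiters, safety managers and workers. Open it only when screening, consent and the on-site baseline are complete for the workers recruited at that visit. Include stage of change and quit ladder in that on-site baseline.
- Allow same-day delivery only after the assignment has been opened.
- Record whether any worker enrolled at a site after its arm was revealed, since a return visit cannot be concealed.
- Report eligible and consented numbers by arm and site as the willingness measure.

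The cost is one sealed release per site, some protocol wording and a slightly longer minimum on-site baseline. There would be fewer same-day deliveries, and some workers would be missed on day 2, which matters in a mobile workforce. Next-day delivery is, however, already the default, and the recruitment text of Section 5 already asks for availability on the following two days, although the lists in Sections 4 and 10 omit this.

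If recruitment is already finished, as the past tense of the Data Analysis section suggests, sealing is no longer possible. The report should then state who knew each site's arm and when, and give the consent numbers by arm.

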Sample Size: Major goals of this pilot study are to explore acceptability of our intervention. These data also will help us to estimate the intervention’s effect size to help determine sample size needs for a future full-scale RCT. We will follow the general rule of thumb and recruit at least 126 participants (63 per group) to estimate the parameters. We will use a two-group comparison of proportions at the two-tailed alpha level and assume that the intra-cluster correlation will be low (0.01). This sample size will allow us to detect a 22% difference between the two groups (a moderate effect size of 0.46) at the two-tailed 0.05 alpha with 80% power. Expecting 20% attrition rate this will leave us with a sample of 51 subjects per group. We will, however, include all randomized participants in assessment of endpoints. We realize limitations of using pilot data to power subsequent studies, related to the inherent imprecision of estimates with small sample sizes. It is important to note, though, that our sample size is large enough to estimate the effect with a reasonably tight confidence interval, and we will not rely exclusively on this effect to estimate power, but will also make use of the extant literature.

6) Data and Specimen Banking*

The following self-reported measures will be obtained specifically for research purposes. These data will be stored in stored on a password-protected computer accessed only by approved study personnel.

- i. Demographic Data and Work Characteristics: This will include: Age, ethnicity, native borne, non native born, acculturation, income, education, health insurance status, and job activities.
- ii. Fagerstrom Test for Nicotine Dependence (FTND): All participants will be given the FTND to assess nicotine dependence. This instrument has been widely tested and used in smoking studies.
- iii. Tobacco Use History: This will include: age when the participant began smoking, number of years as a smoker, the number of cigarettes smoked per day, whether the participant had made a quit attempt in the last year, the number of past year quit attempts, and the number of last year successful quit attempts (defined as being quit for at least one month).

STUDY PROTOCOL AND ANALYSIS PLAN

- iv. Depressive Symptomatology: will be assessed with the Center for Epidemiologic Studies Depression Scale (CES-D; Radloff, 1977; Thomas et al., 2001).

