Quality Assurance- Our research team is well versed in quality assurance processes for intervention studies.^{44,45,59} Following the strategy suggested by Sechrest,⁶⁹ evaluation of any treatment program should involve satisfactory answers to three questions: 1) was the intervention both standardized and delivered as intended to the participant? 2) if so, did the participants receive it? and 3) if so, was the intervention efficacious in changing behavior? Sechrest's 3rd question involves the evaluation of outcomes, which is outlined in the Data Analysis section below. However, Sechrest's 1st and 2nd questions address treatment implementation issues. To ensure standardization of intervention content and delivery, we will use standardized treatment manuals/procedures developed particularly for this study. Participants will respond to a brief questionnaire at baseline and the 3- and 6- month follow-up to assess whether key points were learned, including the techniques and information discussed in the intervention sessions. Standard procedures will be used for instrument development, protocol and forms, and data management (e.g. entry, reconciliation, updating, and data security and confidentiality). Additionally, we will audiotape a random sample of 10% of counseling sessions for review and feedback. Participants will be asked for permission to audiotape these selected sessions as part of the consent process.

Data Analysis

The analyses of the outcomes were mainly descriptive. Chi-square tests and between-group t-tests were used to compare between-group differences in baseline characteristics, and indices of treatment implementation, adherence, and retention. Intra-class correlation coefficients were used to adjust for clustering within sites.⁵⁵ This adjustment accounted for within-site clustering of workers characteristics at each of the 17 participating sites in the trial. Chi-square tests were used to compare cessation rates in the two arms. Analyses were performed on an intention-to-treat basis, with individuals with missing outcome data or self-reported abstinence not confirmed by eCO at 6-month follow-up classified as not quit. Logistic regression analyses were conducted to assess baseline predictors of prolonged abstinence at 6-months.

8) Risks to Subjects*

Potential risks and adverse effects of the study medication will be explained to each participant when informed consent is obtained. Each participant will be instructed to

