To avoid intervention contamination within participating construction worksites, the RCT design will be a two-group cluster randomized design with seven sites per group. Our resources for this R21 allow seven subjects per group. We assume that the intra-cluster correlation will be low (0.01). We will use a two-group comparison of proportions at the two-tailed alpha level. Assuming that 10%-15% of the control group and 25% of the intervention group respond to the intervention, we will have 23% power to detect a 10% difference and 50% power to detect a 15% difference. To achieve 80% power

STUDY PROTOCOL AND ANALYSIS PLAN

for a 10% and 15% difference under the same assumptions would require sample sizes of 64 and 16 subjects per site, respectively.

12) Confidentiality

Participant names will be replaced with ID numbers and a key linking the two will be kept separate from other data and accessed only by Drs. [name] and [name]. Survey data will be stored on Dropbox and accessible only by approved study personnel. Survey data from the RCT will be stored and managed in REDCap. These data will be stored for the duration of the study protocol and until all data analysis is complete and manuscripts have been published.

13) Provisions to Protect the Privacy Interests of Subjects

Participants will interact with only a limited number of approved study personnel and will be assured that their personal information will be kept private, will be used only for research purposes, and will not be accessible to non-study personnel.

14) Consent Process

Verbal consent will first be obtained after potential participants are screened on site. Those who verbally consent will then sign a written consent before the intervention begins. Because we are recruiting Hispanic participants the consent documents will be available in both English and Spanish.

STUDY PROTOCOL AND ANALYSIS PLAN

References

1. [name] DJ, Fleming LE, Arheart KL, et al. Smoking rate trends in U.S. occupational groups: the 1987 to 2004 National Health Interview Survey. *J Occup Environ Med.* Jan 2007;49(1):75-81.
2. [name] DJ, Fleming LE, McCollister KE, et al. Healthcare provider smoking cessation advice among US worker groups. *Tob Control.* Oct 2007;16(5):325-328.

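### At 63 per group the stated effect size of 0.46 has about 73% power (70% with the plan's ICC), not 80%, and the two sample-size passages describe different trials

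*Combined protocol and SAP*

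**What the plan says.** Two places deal with sample size.

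- **Section 5, Sample Size.** The plan will "recruit at least 126 participants (63 per group) to estimate the parameters", on a rule of thumb. For a two-tailed comparison of two proportions with ICC 0.01, it says this number will "detect a 22% difference between the two groups (a moderate effect size of 0.46) at the two-tailed 0.05 alpha with 80% power". It gives no control or intervention rate and does not define the effect size. It expects 20% attrition, leaving 51 per group, but adds: "We will, however, include all randomized participants in assessment of endpoints". It also says that "our sample size is large enough to estimate the effect with a reasonably tight confidence interval".
- **Section 11, Local Number of Subjects.** Seven sites per group, the same ICC, and "Our resources for this R21 allow seven subjects per group". "Assuming that 10%-15% of the control group and 25% of the intervention group respond to the intervention", it states 23% power for a 10-point difference and 50% for a 15-point difference. It says 80% power would need 64 and 16 subjects per site respectively.

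Two other places bear on the point. The recruitment text in Section 5 says: "Our target sample size is up to 150 Hispanic smokers". The Data Analysis text in Section 7 is by intention to treat, with "individuals with missing outcome data or self-reported abstinence not confirmed by eCO at 6-month follow-up classified as not quit", and refers to 17 participating sites.

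**The concern.** The Sample Size sentence fixes five things at once: n, the test, the difference, the effect size and the power. Any four of them can be used to check the fifth, and the check fails for the effect size. The control rate that would reconcile 22 points with 0.46 is not printed, and the rates in Section 11 do not supply it. Section 11 then gives powers that seem to belong to a smaller trial.

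A reader therefore cannot tell what 126 participants can detect, or whether the power statements refer to 98 or 126 people. This matters because the plan says the pilot will help to size a full trial.

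**Working it through.** **Inputs.** From Section 5: 63 per group, two-tailed alpha 0.05, effect size 0.46, 22 points, ICC 0.01 and at least 14 sites. From Section 11: seven sites per arm, control 10%-15%, intervention 25%. At 126/14 = 9 per site the design effect is 1 + 8 × 0.01 = 1.08, so the effective n is 63/1.08 = 58.3 per group. All formulas are normal approximations with z = 1.960 and 0.842.

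**1. The plan's 80% for effect size 0.46.** Take 0.46 as Cohen's h, the difference of 2·arcsin√p. Power = Φ(h·√(n/2) − 1.960).

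| n per group | Design effect | Power for 0.46 |
|---|---|---|
| 63 | 1 | Φ(2.582 − 1.960) = 73.3% |
| 63 | 1.08 | Φ(2.484 − 1.960) = 70.0% |
| 63 (126 over 17 sites, 7.41 per site) | 1.064 | 70.6% |
| 51 (after attrition) | 1 | 64.2% |
| 75 | 1 | 80.4% |
| 75 (7 sites per arm) | 1.097 | 76.7% |

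The n for 80% power is 2 × (1.960 + 0.842)²/0.46² = 74.2, so 75 per group. The effect size with 80% power at 63 per group is 2.802 × √(2/63) = 0.50, or 0.52 with the design effect.

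Two calculations come close to the printed figure, but neither uses the stated inputs. One is 75 per group without ICC, which is the 150 ceiling and not 126. The other is a one-sided 0.05 test at 63 per group with the ICC (79.9%), but the text says two-tailed.

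**2. Does 22 points equal 0.46?** Solving h(p, p + 0.22) = 0.46 gives p = 26.2%, with a mirror solution at 51.8%. Dividing by a pooled SD instead gives 24.4%. At Section 11's control rates, h is 0.56 (10% vs 32%) and 0.51 (15% vs 37%).

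**3. Power for 22 points itself.** Power = Φ{[Δ√n − 1.960·√(2p̄(1−p̄))]/√(p₁q₁ + p₂q₂)} with n = 58.3. For 10% vs 32% this is Φ[(1.680 − 1.129)/0.555] = 84.0%.

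| Control rate | Power for 22 points, 63 per arm, with ICC |
|---|---|
| 10% | 84% |
| 13.2% | 80% |
| 15% | 78% |
| 26% | 70% |

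**4. Section 11's powers.** The same formula at 7 sites × 7 subjects = 49 per arm, without ICC:

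- 15% vs 25%: Φ[(0.700 − 1.109)/0.561] = 23.3%
- 10% vs 25%: Φ[(1.050 − 1.053)/0.527] = 49.8%

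These are the stated 23% and 50%. With the ICC (design effect 1.06) they are 22.2% and 47.5%, or 22.7% and 49.0% with an unpooled variance. At 63 per arm with the ICC they are 26.9% and 57.0%. With literally seven per group they would be about 7% and 11%, so that phrase appears to be a slip for seven per site.

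**5. Section 11's per-site numbers.** With seven sites per arm and ICC 0.01, 80% power needs 16-17 per site for 10% vs 25%, depending on the variance formula, and 55 for 15% vs 25%. The plan prints 16 and 64. Its formula is not stated, so this is a figure to recheck and not a shown error.

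**6. Precision.** The expected 95% CI half-width is 1.960 × √[(p₁q₁ + p₂q₂) × 1.08/63]. It is 14.4 points for 15% vs 25% and 13.5 points for 10% vs 25%, about as wide as the differences assumed.

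**The case against.** The strongest reply is that the plan never defines its effect size. If 22 points is divided by the SD of the intervention arm, 13% vs 35% gives 0.22/√(0.35 × 0.65) = 0.461. The power for that contrast at 63 per arm with the ICC is 80.3%, and 13% lies within Section 11's range. Every figure in the sentence then agrees. That definition is unconventional, however, and nothing in the plan points to it. The two usual readings, Cohen's h and the pooled-SD difference, both fail. What stands is that 73% and 70% depend on a conventional reading of an undefined term, which is itself a reason to define it.

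Second, the operative claim is about a difference in proportions, and 22 points with 80% power is close to right at control rates of 10%-15%. This stands. The error lies in the effect size attached to the claim and in the missing control rate.

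Third, Section 11 errs on the cautious side, since its powers are lower than those at 63 per arm. Also true, but it still describes 98 participants and not 126.

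Fourth, the weight is small. The 126 is put down to a rule of thumb, the main outcomes concern feasibility, the analysis is mainly descriptive, and the plan admits imprecision and says it will not rely on this effect alone. This limits the harm but does not correct the figures.

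**Conclusion.** The concern holds. With 0.46 read as a conventional standardized difference, the stated 80% is 73% before clustering and 70% with the plan's own ICC. The effect size that 63 per group detects with 80% power is 0.50, or 0.52 with the ICC. The pairing of 22 points with 0.46 implies a control rate near 26% (24% with a pooled SD), which is outside the 10%-15% the plan assumes. Section 11's powers are for 49 per arm.

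The conclusion rests on normal approximations, equal site sizes and 14 sites; using 17 sites changes 70.0% to 70.6%. Reading Section 11 as seven per site is an inference, but its printed powers support it.

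This should be corrected, though it does not threaten the trial: neither the design nor the recruitment target depends on it.

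**What to change.** Replace the two passages with one statement, for example:

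> At the minimum of 126 participants (63 per arm, 7 sites per arm, about 9 per site), with ICC 0.01 (design effect 1.08) and two-sided alpha 0.05, the trial has 80% power for an effect size (Cohen's h) of about 0.52, such as 10% vs 31% or 15% vs 38% abstinent among all randomized participants, with missing counted as not quit. Power is about 27% for 15% vs 25% and 57% for 10% vs 25%. The expected 95% CI half-width for these two differences is about 14 points.

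In addition:

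- If the sponsor keeps 22 points, give its control rate and power (84% at 10%, 78% at 15%), and define the effect size.
- Say whether 22 points is a difference among all randomized participants. If it is among completers, 20% missing counted as not quit shrinks it to 0.8 × 22 = 17.6 points. Power with the ICC is then about 73% (8% vs 25.6%) or 65% (12% vs 29.6%).
- Correct the seven-per-group phrase, recheck the 64 per site and name the formula used.
- Put the half-width beside the claim about a tight interval.

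The cost is wording only, with no added participants or sites. The stated detectable effect size rises from 0.46 to 0.52, and the powers quoted for 10 and 15 points rise slightly.
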